7.2 Clinical Laboratory Parameters

Safety clinical laboratory parameters were collected and assessed, but only used to identify adverse events. Clinical laboratory parameters will be summarized by treatment group and time point.

7.3 Vital Signs

Changes in vital signs (including systolic and diastolic blood pressure [mmHg], heart rate [beats per minute], peripheral 02 saturation (%), respiration frequency (numerical value), temperature (in Celsius degrees) and weight [kg]) will be summarized by treatment group and time point during admission.

8 Statistical Software

All statistical analyses will be done in Stata SE version 17 (StataCorp LLC, College Station, TX, USA).

9 References

- Bauer P. Multiple testing in clinical trials. Statistics in Medicine 1991; 10:871-890.
- ICH E9(R1) Addendum on estimands and sensitivity analysis in clinical trials. *International council for harmonisation of technical requirements for pharmaceuticals for human use*; 2019.
- Senn S. Statistical Issues in Drug Development. John Wiley & Sons, 2007.
- Williams DA. A test for differences between treatment means when several dose levels are compared with a zero dose control. *Biometrics* 1971; 27:103-117.

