|---------------------------------------|---|---|---|---|---|---|
| Total
Cholesterol                  | X | Х | Х | Х | Х | X |
| BIOBANKING:                           |   |   |   |   |   |   |
| 4x EDTA                               | X | Χ |   | Χ | Χ | Х |
| 1x Serum                              | X | Χ |   | Χ | Χ | Χ |
| 1x Plasma                             | X | X |   | Χ | Χ | X |
| 2x CPT                                | X | Χ |   | Χ | Χ | Χ |
| Urine, faeces, saliva,buccal swabs ** | x | x |   | x | x | х |

\* Prior to administration of intervention drug

Table 2: Timing of inclusion and procedures.

|                                      | Screening
period | Treatment Period At inclusion (1), day 3, 7 [i] And on discharge (DC) | Mid-
treatment
follow-up
phone call | Last week
of
treatment
visit at 90
days+/- 10 | End of
study
visit ca
65 wks. | Withdrawal
visit | Follow
up
period |
|--------------------------------------|---------------------|--|--|---|--|---------------------|------------------------|
| Screen patients [ii]                 | Х                   |  |  |   |  |                     |                        |
| Informed consent                     | Х                   |  |  |   |  |                     |                        |
| Inclusion + exclusion criteria       | Х                   |  |  |   |  |                     |                        |
| Medical history, prior treatment.    | Х                   |  | Х  |   |  |                     |                        |
| Treatment dispensed/returned         |                     | 1  |  | ×   |  | х                   |                        |
| Concomitant medication[iii]          | Х                   | 1-7, DC  | Х  | Х   | Х                                      | Х                   |                        |
| Physical examination [iv]            | Х                   | 1-7  |  | Х   | х                                      | Х                   |                        |
| Vital signs [v]                      | Х                   | 1-7  |  | Χ   | X                                      | Х                   |                        |
| Tests/questionnaires [vi] |                     | 1-7,   |  | Х   | Х                                      | Х                   |                        |

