| Adverse events                       |                     | 1-7, DC  | Χ  | Χ   | Χ                                      | X                   | X                      |
| Survival assessment                  |                     | 1-7, DC  | Х  | Х   | Х                                      | Х                   | х                      |

(DC: Discharge)

\*\*Selected number of patients only

i] And every 7th day onwards if still hospitalized.

ii] All ICU patients and patients on the following medical wards are screened: Infectious diseases, internal medicine, pulmonary medicine and acute medicine. See also own section on screening.

iii] Antibiotics and vitamin B3 containing drugs only.

iv] Full physical examination of all major organ systems.

v] Blood pressure, pulse, temperature, respiration rate and 02 saturation.

[vi] See table 3 below for details.

Table 3: Overview of scoring forms and other assessment methods  $^{**}$ 

| CLINICAL TEST/scoring systems                                    | TIMING  |
|--|---|
|  |   |
| EQ5D (filled in by investigator in the presence of the           | 2 weeks prior to admission. On day 1 and on day 90.                     |
| patient).  |   |
|  |   |
| MOCA   | Day 7 and 90 and week 65.   |
| Trail making A   | Day 7 and 90 and week 65.   |
| Trail making B   | Day 7 and 90 and week 65.   |
| Forward and Backward Recall.                                     | Day 7 and 90 and week 65.   |
| NEWS (completed by nursing staff as part of standard treatment). | - Baseline morning and afternoon, day 3 and day 7.                      |
|  |   |
|  |   |
|  |   |
| 4 meter walking test   | At baseline, day 7, day 90 and week 65.                                 |
| Clinical Frailty score (filled in by investigator)               | Pre-baseline, baseline, day 7, day 90 and week 65.                      |
| Grip strength  | At baseline, day 7, at discharge, day 90 and week 65.                   |
|  | (and every occation at hospital).                                       |
| RASS (completed by nursing staff as part of standard             | Day 0, 1, 3, 7 and every 7 th day thereafter for the         |
| treatment of sedated patients).                                  | duration of stay in ICU   |
|  |   |
| Charlson comorbidity index (Filled in by investigator)           | Baseline  |

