### 10.5.5 Safety analyses

See SAP.

Tabular safety analyses will be performed for all collected variables.

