2.3 Sample size

Assuming the time of hospitalization after randomization follows a Weibull distribution with a scale parameter λ = 18 and shape parameter κ =2.2 (corresponding to a median of 15 and an IQR of 10 – 21), we need to include 58 patients: 18 in the placebo group, 10 in the 250 mg/day group, 10 in the 500 mg/day group, and 20 in the 1 g/day group) in order to reach approximately 80% power to show a significant dose-response in this study with a maximal reduction in time of hospitalization of 33%. This calculation is based on optimal designs in dose-finding studies according to the MCPMod methodology with three alternative dose-response curves: linear, e-max and exponential (Pinheiro et al., 2014).

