6.5 Assumption Checks and Alternative Analyses

Assumption checks will be performed for the primary and all secondary outcomes according to the statistical methods used to analyzed them.

Weibull and Cox Proportional Hazard Models

The Weibull and Cox proportional hazard regression models assumes that the hazard ratio is constant over time. This will be checked by plotting -log(log(survival)) curves for each treatment against log(analysis time) and assessing if the curves are parallel. If the proportional hazard assumption is deemed to be violated, alternative parametric survival models will be fitted instead. The following survival distributions will be considered: exponential, Gompertz, and lognormal. The goodness-of-fit of each model will be assessed with plots of Cox—Snell residuals against the estimated cumulative hazard function of the residuals, and the one with the best fit will be the chosen model.

Linear Mixed Models

For linear mixed models, we will compare observed and model-predicted outcomes. If we detect a poor-fitting model, we will refit the model with a log-transformation of the outcomes. We do not expect other model-fit problems, due to the simplicity of the model (only a random intercept and a few fixed effects); however, in the unlikely event that we will encounter numerical problems with fitting the model, we will remove the two time point variables and substitute it with a single (linear) variable for time.

Two-sample T test

The discrete numerical outcomes (number of new infections per patient and number of readmissions per patient) are limited to only a few possible values (with no great maximum), and as

such, there is no concern about the distribution of the outcomes, except for the situation where almost all patients have the same number and there is not enough variation in the data to get a meaningful result from the statistical methods. In that case, the outcome will be presented with the table of observed number and percentages in each treatment group in each category only.

7 Safety Analyses

General safety evaluations will be based on the incidence, intensity, and type of AEs, and clinically significant changes in the patient's physical examination findings, vital signs, clinical laboratory results and serum drug concentrations. Safety variables will be tabulated and presented for all patients in the safety set.

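### The vital-sign safety tables stop at discharge, so the scheduled day-90 and week-65 values are not tabulated and any inpatient values after day 7 come only from patients still admitted

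*SAP*

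**What the plan says.** SAP 7.3 lists blood pressure, heart rate, oxygen saturation, respiration, temperature and weight, and says that changes in them "will be summarized by treatment group and time point during admission". No other SAP table uses vital signs measured after discharge.

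The rest of the plan is wider:

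- Protocol Table 2 (section 6.1) marks vital signs at screening, on inpatient days 1-7, at the last-week-of-treatment "visit at 90 days+/- 10", at the end-of-study visit at about 65 weeks, and at the withdrawal visit. Its note [v] defines them: "Blood pressure, pulse, temperature, respiration rate and 02 saturation".
- Note [i] to the inpatient column heading extends assessments to every seventh "day onwards if still hospitalized".
- Protocol 10.5.5: "Tabular safety analyses will be performed for all collected variables".
- SAP section 7, opening paragraph: "Safety variables will be tabulated and presented for all patients in the safety set".
- SAP 7.2, by contrast, has no admission limit: "Clinical laboratory parameters will be summarized by treatment group and time point".
- SAP 2.7 already defines windows for days 14, 21 and 28, day 90 and week 65.

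**The concern.** Two consequences follow from the admission limit.

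The first is omission. Dosing runs for three months, mostly after discharge. A modest shift in blood pressure or heart rate that appears with longer exposure would not show in any planned vital-sign table, although the visits at which it could be seen are scheduled.

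The second concerns the time points that remain. After day 7, any inpatient value exists only for a patient who has not been discharged, and time to discharge (to being medically fit for it, in SAP section 5) is the primary outcome. If NR shortens the stay, the patients left in each arm are selected differently, and a by-arm summary of them is no longer a comparison of randomized groups.

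**Working it through.** **Inputs.** From SAP 2.3: stay follows a Weibull distribution with scale 18 and shape 2.2, stated median 15 and IQR 10-21; groups of 18 (placebo), 10, 10 and 20 (1 g/day); power is planned "with a maximal reduction in time of hospitalization of 33"%. From Protocol section 3: three months of treatment, taken here as 90 days. A 33% reduction is taken as one third, which gives scale 18 × 2/3 = 12. Deaths are ignored.

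**Step 1: reproduce the plan's figure.** Quantile = 18 × (−ln(1−p))^(1/2.2). For p = 0.25, 0.50 and 0.75 this gives 10.2, 15.2 and 20.9, matching the stated 10, 15 and 21.

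**Step 2: share of dosing covered.** Mean stay = scale × Γ(1 + 1/2.2) = scale × 0.8856.

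- No effect: 18 × 0.8856 = 15.9 days; 15.9/90 = 18%.
- Stay one third shorter: 12 × 0.8856 = 10.6 days; 10.6/90 = 12%.

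**Step 3: who is still in hospital.** S(t) = exp(−(t/scale)^2.2). At day 14, for example, (14/18)^2.2 = 0.575 and exp(−0.575) = 0.56; (14/12)^2.2 = 1.404 and exp(−1.404) = 0.25.

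| Day | Placebo, share | Placebo, expected of 18 | 1 g/day, share | 1 g/day, expected of 20 |
|---|---|---|---|---|
| 3 | 98% | 17.7 | 95% | 19.1 |
| 7 | 88% | 15.9 | 74% | 14.7 |
| 14 | 56% | 10.1 | 25% | 4.9 |
| 21 | 25% | 4.4 | 3% | 0.65 |
| 28 | 7% | 1.3 | 0.2% | 0.03 |
| 90 | about 0 | about 0 | about 0 | about 0 |

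Days 3 and 7 still hold most patients. From day 14 the remaining sets differ by arm. Under this model no one is in hospital at day 90, so an admission-only table has no day-90 column. If NR did not change the stay, the expected shares would be those of the placebo column in every arm.

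**Step 4: are vital signs taken weekly after day 7?** Probably, but the text is not firm. The vital-signs row in Table 2 reads 1-7, and the every-seventh-day rule is a note to the column heading. The *Weekly* column in Table 1 covers only laboratory tests and biobanking. SAP 2.7 lists days 14, 21 and 28. Step 3 therefore applies to vital signs if they are recorded weekly, and to the weekly laboratory values in any case.

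**The case against.** **Much of the safety information is captured elsewhere.** Protocol 8.5 records any unexpected vital sign as an adverse event, 8.4 collects events until 30 days after day 90, and SAP 7.1 tabulates treatment-emergent events by group. This stands for individual abnormal values. It does not show a shift in group means that stays within expected limits.

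**Blood pressure is covered.** Protocol 10.5.4 plans a comparison of blood pressure from inclusion to the end-of-study visit. SAP 1.2 and the outcome table in SAP section 5 leave outcomes outside the main article to the protocol, so this analysis is deferred, not abandoned. It is one vital sign, in an efficacy table.

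**Laboratory values are not affected in the same way.** A reader might infer that SAP 7.2 also drops day-90 results. It does not: it has no admission limit, and Table 1 schedules laboratory tests at day 90. Only its weekly inpatient columns share the selection problem.

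**A beneficial drug would look harmful.** A reader might infer this from Step 3, and the documents do not support it. Suppose a vital sign correlates 0.3-0.5 with stay and NR does not affect it; neither assumption has a source in the documents. Normal scores (using 33% exactly, scale 18 × 0.67 = 12.06) differ between the remaining sets by 0.57 SD at day 14 and 0.94 SD at day 21. Multiplied by 0.3-0.5, that is 0.17-0.29 SD and 0.28-0.47 SD. With about 10 v 5 patients at day 14, the standard error of a difference is √(1/10 + 1/5) = 0.55 SD, so the spurious difference is a third to a half of one standard error. At day 21 fewer than one NR patient is expected. If NR speeds recovery it may also improve vital signs, and if discharge depends on vital signs the remaining patients may look alike. The tables are descriptive and show changes, not levels.

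**Day 90 is not a clean comparison either.** Values come from attenders. The window is ±10 days in Table 2, ±7 in Protocol 6.2.3, and +90/−30 in SAP 2.7, which runs from day 60 to day 180. Some values could be taken well after dosing ends. This limits what a day-90 column can show but is not a reason to leave it out.

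**Conclusion.** SAP 7.3 is narrower than Protocol Table 2, Protocol 10.5.5 and the opening of SAP section 7. As written, the vital-sign tables cover about 12% to 18% of the dosing period under the SAP's own planning model and contain nothing from the end of treatment. This follows from the text and the planning figures alone.

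The selection point holds in a limited form. If vital signs are recorded weekly, the summaries from day 14 on do not compare randomized groups when NR changes the stay. The counts (10.1 v 4.9 at day 14, 4.4 v 0.65 at day 21) are planning-model expectations at the maximal assumed effect, not trial data. The size and direction of any bias are not established.

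This is a free improvement: a wording gap in descriptive safety tables. The primary analysis, sample size and power are unaffected.

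**What to change.** In SAP 7.3:

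1. Delete the words *during admission*.
2. Tabulate change from baseline by treatment group at day 3, day 7, day 90 and week 65, with n per arm at every time point. Show withdrawal-visit values separately. Weight is not among the vital signs in Table 2 note [v], so state at which visits it exists.
3. Label any inpatient vital-sign or laboratory summary after day 7 (SAP 7.2 and 7.3) as conditional on continued admission.

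The cost is one or two more descriptive tables from data already scheduled. The day-90 and week-65 columns remain subject to death, non-attendance and the wide SAP windows (week 65 is ±180 days). The documents give no rate for death or non-attendance, so the n per arm matters.

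Tables of each patient's worst value are a possible addition but a trade-off: the worst value depends on the number of measurements, and so on length of stay. They are not needed for this fix.
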